The neutralizing antibody will be summarized for each individual concentration groups 1.5, 3, 6, 9 ug/mL and total by descriptive statistics including mean, standard deviation (SD), median and range (min & max) at each scheduled timepoint. Individual and mean plasma concentration-time profiles of neutralizing antibody will also be plotted.

Assessment of IL4R Status

IL4R results will be summarized according to the categories below by descriptive statistics including mean, standard deviation (SD), median and range (min & max).

- By concentration of MDNA55 administered (1.5, 3, 6, 9 µg/mL) as well as overall
- By low and high total dose of MDNA55 administered (based on median)

7.7.4 Other Efficacy Endpoints Analyses

Duration of response (DOR)

Duration of response (DOR) is defined as the time from first response PR or better until confirmed disease progression (PD) or death among those subjects achieving a complete response (CR) or partial response (PR) to treatment. Responders alive and progression-free at the time of the analysis will be censored at the time of the last radiologic assessment demonstrating lack of progression or, if during the follow-up period, the time of last contact indicating lack of progression.

DOR = Date of event/censoring - Date of first response +1

DOR rates at 6, 9, and 12 months and their exact 95% CI for the DOR along with the estimate for median and its 80%, 90% and 95% CI, will be produced using KM method. All derived efficacy variables will be displayed in a data listing. KM estimates of DOR will also be presented graphically at 6, 9 and 12 months.

DOR analysis will be based on responders in mITT population. Use of sub-therapeutic doses of Avastin will also be considered in determination of DOR (and may result in a variant of the DOR being calculated).

Duration of Clinical Benefit (DOCB)

Duration of Clinical Benefit (DOCB) is defined as the time from first response or disease stabilization until disease progression or death among those subjects achieving a complete response (CR), partial response (PR), or stable disease (SD). Censoring will be performed in a fashion similar to DOR.

DOCB = Date of event/censoring - Date of first response +1

The analysis will be similar to DOR. All derived efficacy variables will be displayed in a data listing. The Kaplan-Meier estimates of DOCB will be shown in a separate graph.

DOCB analysis will be based on responders in mITT population. Use of sub-therapeutic doses of Avastin will also be considered in determination of DOCB (and may result in a variant of the DOCB being calculated).

Time to Tumor Progression (TTP)

TTP is defined as the time between the date of catheter placement and the date of first evidence of disease progression (PD). For subjects who do not experience tumor progression by the time of data cut-off, TTP will be right censored at the date of last adequate disease response assessment.

TTP = Date of event/censoring - Date of catheter placement +1

The analysis will be similar to DOR or DOCB. All derived efficacy variables will be displayed in a data listing. The Kaplan-Meier estimates of TTP will be shown in a separate graph.

The analysis will be based on mITT population. Use of sub-therapeutic doses of Avastin will also be considered in determination of TTP (and may result in a variant of the TTP being calculated).

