9.2.5.3 Other Efficacy Variables and Analyses

DOR will be summarized using the Kaplan-Meier method, including graphical displays. DOR will be calculated only for the subset of subjects with a response (CR or PR), and it will be defined as the time (in weeks) from first response until radiologic disease progression or death from any cause. Responders alive and progression-free at the time of the analysis will be censored at the time of the last radiologic assessment demonstrating lack of progression or, if during the follow-up period, the time of last contact indicating lack of progression.

DOCB will be summarized using the Kaplan-Meier method, similar to DOR. DOCB will be calculated only for the subset of subjects with a stable disease or better (CR, PR, or SD), and it will be defined as the time (in weeks) from first response until radiologic disease progression or death from any cause. Censoring will be performed in a fashion similar to DOR.

Additional, exploratory, efficacy variables may include ORR and PFS based on the Investigator's assessment of response and other time-to-event endpoints (e.g., time to post-study treatment of GB). Analyses will also be conducted by IL4R stratum, including examination of the treatment effect by IL4R level.

[figure not shown]
Efficacy analyses will also explore subject subsets (procedural success, IL4R level, sequence number by site [learning], tumor size, tumor coverage, time of infusion, maximum flow rate, number of catheters, percentage of planned infusate administered, KPS, gender, age, steroid use, immune status) and response by other applicable criteria. Subgroup and sensitivity analyses comparing subjects included before and after protocol version 3.0 may be explored.

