4.3 Other Efficacy Endpoints

- Duration of response (DOR). Defined as the time from first response until disease
 progression (per RANO-based criteria and as determined by an independent central
 review) or death among those subjects achieving a complete response (CR) or partial
 response (PR) to treatment;
- Duration of clinical benefit (DOCB). Defined as the time from first response or disease stabilization until disease progression (per RANO-based criteria and as determined by an independent central review) or death among those subjects achieving tumor control: complete response (CR), partial response (PR), or stable disease (SD);
- To determine the Tumor Control Rate (TCR) defined as the proportion of subjects in whom the best overall response is determined as complete response (CR), partial response (PR) or stable disease (SD) based on different sets of imaging-based response criteria. Use of sub-therapeutic doses of Avastin will also be considered in determination of TCR (and will result in a variant of the TCR being calculated);
- Time to Tumor Progression (TTP). Defined as the time from treatment until tumor progression; does not include death.

4.4 Exploratory Endpoints:

 To determine the relationship between efficacy endpoints (i.e., OS, PFS, DOR, DOCB, TTP) and tumor response category using different sets of imaging-based response criteria;

- To determine the relationship between efficacy endpoints (i.e., OS, PFS, DOR, DOCB, TTP, TCR) and IL4R expression status;
- To determine the relationship between efficacy endpoints (i.e., OS, PFS, DOR, DOCB, TTP) and various prognostic factors (i.e., age, sex, KPS, MGMT status, etc);
- To determine the relationship between efficacy endpoints (i.e., OS, PFS, DOR, DOCB, TTP) and use of concomitant medication (i.e., Avastin, steroids);
- To determine the relationship between efficacy endpoints (i.e., OS, PFS, DOR, DOCB, TTP) and various treatment and drug distribution parameters (i.e., MDNA55 concentration, total dose, volume of infusion, percent tumor coverage, etc.);
- To assess the performance of Brainlab catheter during infusion through real time MRI monitoring;

Note: All exploratory analyses will be conditional upon data being available.

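### SAP 7.7.4 computes duration of clinical benefit from the date of first response in responders only, which contradicts its own definition covering stable disease

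*SAP*

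**What the plan says.** The definition sentence in SAP 7.7.4 makes DOCB the "time from first response or disease stabilization until disease progression or death" among subjects with CR, PR or SD. SAP 4.3 describes the same group as those "achieving tumor control: complete response (CR), partial response (PR), or stable disease (SD"). The protocol synopsis and Protocol Table 8 agree with both on the start and on who is included.

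The operational lines that follow in SAP 7.7.4 are narrower. The formula is "DOCB = Date of event/censoring - Date of first response +1", and the population line reads "DOCB analysis will be based on responders in mITT population". In the same section, DOR is the "time from first response PR or better until confirmed disease progression (PD) or death".

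Protocol 9.2.5.3 states that "DOCB will be calculated only for the subset of subjects with a stable disease or better (CR, PR, or SD"), but it then starts the clock at first response and does not mention stabilization.

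**The concern.** A subject whose best response is SD has no date of first response and is not a responder in the sense used for DOR and ORR. The formula therefore returns nothing for that subject, and the population line removes the subject anyway. DOCB exists to add these subjects to the picture that DOR gives. If the operational lines are followed, it adds none of them.

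The effect reaches beyond one Kaplan-Meier curve. SAP 4.4 relates DOCB to response category, IL4R status, prognostic factors, concomitant Avastin and steroids, and drug distribution. Protocol 7.3.1 also evaluates it against IL4R staining intensity. Each of these analyses would run on CR and PR subjects only. One group that the protocol deliberately keeps on study would be hit directly: under Protocol 8.1.3, subjects whose resected tissue shows no recurrent tumor are assigned a best response of SD after surgery. Those without an earlier CR or PR would have no DOCB.

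**Working it through.** The plan gives no figure for DOCB, so there is nothing to reproduce. The check is a comparison of the texts.

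| Place | Clock starts at | Subjects included |
|---|---|---|
| Protocol synopsis; Protocol Table 8 | first response or stabilization | CR, PR, SD |
| SAP 4.3 | first response or stabilization | CR, PR, SD |
| SAP 7.7.4, definition sentence | first response or stabilization | CR, PR, SD |
| SAP 7.7.4, formula and population line | first response | mITT responders |
| SAP 7.7.4, DOR | first response (PR or better) | mITT responders |
| Protocol 9.2.5.3 | first response | CR, PR, SD |

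1. The operational DOCB row and the DOR row have the same start and the same set. Apart from the endpoint name, the formulas and population lines match.
2. Response means CR or PR in the DOR text and in the ORR definition (SAP 7.7.2, Protocol 8.1.3). Where the SAP means SD or better, it says so, as in the two best-response groups of SAP 7.7.3.
3. It follows that an SD-only subject has no start date and is outside the set. The number of subjects in the DOCB analysis equals the number in the DOR analysis.
4. One difference from DOR remains in the SAP: its DOR text requires confirmed progression and its DOCB text does not. Protocol Table 8 requires confirmation for both.
5. No section says how stabilization is dated, or which date governs when SD comes before a response. For a subject read as SD at Day 30 and PR at Day 90, the two candidate start dates are 90 − 30 = 60 days apart.

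For scale only, with assumed rates that are not from the documents, applied to the planned minimum of 46 evaluable subjects:

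- Share of the intended set lost = SD / (CR + PR + SD).
- Smallest loss, CR/PR 28% and SD 30%: 0.30 / 0.58 = 52%.
- Largest loss, CR/PR 5% and SD 60%: 0.60 / 0.65 = 92%.
- Intended set: from 46 × (0.05 + 0.30) ≈ 16 to 46 × (0.28 + 0.60) ≈ 40 subjects.
- Set under the formula: from 46 × 0.05 ≈ 2 to 46 × 0.28 ≈ 13 subjects.

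The mITT population may differ from 46, but the share lost does not depend on that number.

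**The case against.** The intended endpoint is clear. Four texts agree on it, and one of them is the sentence just above the formula. The two deviant lines look carried over from DOR, and a careful programmer would more likely raise a query than run DOR twice. The word responders could also be meant loosely: the DOCB paragraph omits the PR-or-better qualifier, and SAP 7.7.3 groups SD with CR and PR. Tumor control rate (SAP 4.3) separately reports the proportion with CR, PR or SD.

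Much of this is fair, and silent loss of SD subjects is not a certainty. But the loose reading still leaves an SD-only subject without a start date, and Protocol 9.2.5.3 cannot supply one because it too starts at first response. A query would then be settled in an open-label, single-arm trial, where the choice can be made with outcomes visible. Tumor control rate gives a proportion and says nothing about duration.

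A reader might infer that the protocol repeats the whole fault. It does not: its population is right, and only its start date is incomplete. A reader might also blame the formula for timing SD subjects and responders from different origins in one curve. The definition already permits that by naming two possible starts, so a single origin is a choice the plan should make, not something the formula took away.

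**Conclusion.** The operational lines in SAP 7.7.4 contradict the definition they are meant to implement. Followed as written, they remove every SD-only subject and make the DOCB set the DOR set. That conclusion rests on the text alone.

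The size of the loss depends on response rates that the documents do not give; 52% to 92% holds only over the assumed range. The 60-day gap is likewise an illustration, and it counts as lost time only if the clock is meant to start at the earlier SD reading, which the plan does not say.

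The matter should be corrected, but it is contained. A reader might infer that it weakens the main efficacy result. It does not: DOCB is listed among the other efficacy endpoints, is summarized descriptively, and is not named in the testing hierarchy of Protocol 9.4. The OS, PFS and ORR analyses and the sample size are unaffected.

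**What to change.** In SAP 7.7.4:

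- Replace the population line with: mITT subjects with a best response of CR, PR or SD.
- Replace the formula with: DOCB = date of event or censoring − date of the first scheduled follow-up response assessment (Day 30 visit or later) read as SD or better + 1.
- State that this start applies to all such subjects, including those with SD before a response.
- Exclude the end-of-infusion MRI and the 18-30 hour post-operative MRI as start dates. The latter also records tumor dimensions (Protocol Table 6), so an unqualified rule about the first post-treatment scan could start the clock about a day after infusion and bring DOCB close to PFS.
- Require confirmed progression, as Protocol Table 8 does.

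In Protocol 9.2.5.3, align the start date; the population can stay. The sponsor may justify another anchor for SD, but one has to be stated and applied to every CR, PR and SD subject.

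The cost is two lines of SAP text, the clarifying statements above and a matching protocol clarification. No data collection is added: Protocol 6.4 already provides for central review at each follow-up time point.

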1.4.1 Rationale for Endpoint Methods

Overall Survival is the chosen primary endpoint for this trial as an unequivocal, objective, direct measure of clinical outcome.

In this study ORR will be assessed as a secondary endpoint because MDNA55 shares many properties with immunotherapies, including the possibility of pseudo-progression seen on post-treatment imaging and the possibility of response following prolonged (> 3 months) pseudo-progression (Weber et al., 2003a; 2003b; Okada et al., 2015), both of which can confound the assessment of ORR (Ellingson et al., 2017b). The mode of action of MDNA55 includes initial inflammatory response and necrosis in areas of macroscopic and microscopic infiltrative tumor whereby localized inflammatory responses mimic radiological features of tumor progression with increased enhancement and edema (Weber et al., 2003a; 2003b).

[figure not shown]
Pseudo-progression is an increase in contrast enhancement on MRI without true underlying tumor progression and may be due to tumor necrosis associated with MDNA55's known mechanism or local tissue reaction due to the CED procedure. Subjects with pseudo-progression may develop brain edema, mass effect and other symptoms that are clinically indistinct from typical disease progression. Failure to recognize this phenomenon may result in premature subject withdrawals from the study, prior to establishing evidence of clinical benefit. To minimize these confounding effects, the application of the RANO criteria in this study will include the use of multi-modality imaging assessments for response analysis and allowing of the designation of non-progression status to patients who have no subsequent signs of disease progression on imaging after initially being considered to have progressive disease (PD). Multi-modality assessments include contrastenhanced MRI, diffusion MRI, perfusion MRI, spectroscopic MRI, TRAMs, clinical evaluation and tumor tissue biopsy to aid identification of pseudo-progression during early progressive enhancement on T1 images with contrast. Furthermore, in determining PD, there will be less weight on T2-FLAIR images associated with edema. Worsening of clinical symptoms attributed to edema or increased use of steroids to control edema will not automatically be registered as PD.

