8.1.4 Other Time-to-Event Endpoints

The time-to-event endpoints are defined in Table 8.

Table 8: Efficacy Endpoints

| Endpoint | Definition |
|--|---|
| Overall Survival (OS) at fixed times | OS at 6 (OS-6), 9 (OS-9) and 12 (OS-12) months will be estimated. |
| Progression- Free Survival (PFS) at fixed times | PFS at 6 (PFS-6), 9 (PFS-9) and 12 (PFS-12) months will be estimated. |
| Duration of response (DOR) | The time from first response until confirmed disease progression or death among those subjects achieving a complete response (CR) or partial response (PR) to treatment |
| Duration of clinical benefit (DOCB) | The time from first response or disease stabilization until confirmed disease progression or death among those subjects achieving a CR, PR, or stable disease (SD) |

The use of MRI is mandatory to determine tumor response and to assess when objective progressive disease has occurred (for use in estimating PFS, DOR, and DOCB).

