9.2.2 Analysis Populations

Following quality review of study images mid-way through recruitment, local tissue reactions, inflammation, immune cell infiltration, edema and/or necrosis, subsequent to MDNA55 administration, was observed in some subjects and has been seen to be indistinguishable from possible tumor growth using the imaging techniques adopted from the outset of this study. Therefore, obtaining reliable imaging data for the primary efficacy analysis has been shown to be confounded. Consequently, under protocol version 6.0, the surrogate endpoint Objective Response Rate (ORR) will be assessed as a secondary outcome measure with the median Overall Survival (mOS) becoming the primary variable.

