7.7.2 Secondary Efficacy Analyses

To Assess the Effect of IL4-R Status on Overall Survival (OS)

The secondary efficacy assessment will be to assess the effect of IL4-R status on overall survival (OS). The median OS with its 80%, 90% and 95% confidence interval will be estimated using the KM method, with IL4-R status as strata.

Survival rates at 6, 9, and 12 months and their exact 95% CI for the OS along with the estimate for median and its 80%, 90% and 95% CI, will be produced using KM method. KM estimates of OS will also be presented graphically at 6, 9 and 12 months for each IL4-R stratum.

Objective Response Rate (ORR)

Objective Response Rate (ORR) is the proportion of subjects who achieved a complete response (CR) or partial response (PR) (by RANO-based criteria using both 2-dimensional and volumetric assessments and which may include the incorporation of advanced imaging modalities based on availability of data) out of all treated subjects. Use of sub-therapeutic doses of Avastin will also be considered in determination of ORR (and will result in a variant of the ORR being calculated). Objective response rate will be summarized using percentages along with two-sided 80%, 90% and 95% Clopper-Pearson CI at scheduled time points. Subjects with baseline assessments but no post-treatment assessments will be excluded from the ORR analysis. In addition, the number and percent of subjects by response CR or PR will be summarized. All derived efficacy variables will be displayed in a data listing.

Progression Free Survival (PFS)

Progression Free Survival (PFS) is measured as the time from catheter placement to the date of confirmed disease progression or death from any cause, whichever occurs first. For subjects who are not known to have died or progressed as of the data-inclusion cut-off date, PFS time will be censored at the time of the last radiologic assessment demonstrating lack of progression or, if during the follow-up period, the time of last contact indicating lack of progression.

PFS= Date of disease progression/death – Date of catheter placement +1

PFS rates at 6, 9, and 12 months and their exact 95% CI for the PFS along with the estimate for median and its 80%, 90% and 95% CI, will be produced using KM method. All derived efficacy variables will be displayed in a data listing. KM estimates of PFS will also be presented graphically at 6, 9 and 12 months.

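### SAP 7.7.4 dates TTP to the first evidence of PD and ends DOCB at unqualified progression, while PFS and DOR need confirmed PD, so a PD that is later cancelled can count as an event

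*SAP*

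**What the plan says.** **TTP.** SAP 4.3 lists it as an other efficacy endpoint: "Defined as the time from treatment until tumor progression; does not include death". That wording does not say whether progression must be confirmed. SAP 7.7.4 is more specific: "TTP is defined as the time between the date of catheter placement and the date of first evidence of disease progression (PD". For subjects without progression, "TTP will be right censored at the date of last adequate disease response assessment". The protocol has no TTP endpoint.

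**PFS.** SAP 7.7.2 uses the "time from catheter placement to the date of confirmed disease progression or death from any cause". Protocol 8.1.2 also requires confirmed objective progression. Protocol 9.2.5.2 describes radiologic or neurologic progression without the word confirmed.

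**DOR.** SAP 7.7.4 ends it at confirmed PD or death.

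**DOCB.** SAP 7.7.4 ends it at disease progression or death, with no mention of confirmation. Protocol Table 8 (section 8.1.4) reads "The time from first response or disease stabilization until confirmed disease progression or death". The protocol synopsis and section 9.2.5.3 omit confirmation.

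**Why confirmation matters in this trial.** Protocol 9.2.2 says that the post-treatment tissue reaction in some subjects "has been seen to be indistinguishable from possible tumor growth using the imaging techniques adopted from the outset of this study". Protocol 1.4.1 says that applying RANO here includes allowing the "designation of non-progression status to patients who have no subsequent signs of disease progression on imaging" after an initial PD. Protocol 4.4 adds that PD is not confirmed if a later scan shows disease control. Protocol 8.1.3 names initial and confirmed PD as separate states.

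**The concern.** The protocol treats a first reading of PD as provisional and lets later imaging cancel it. PFS and DOR in the SAP follow that approach. The TTP sentence does not, and DOCB leaves the question open. A programmer who reads 7.7.4 and sees *confirmed* for DOR and *first evidence* for TTP would reasonably code the two differently.

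A flare that reaches the PD threshold and then resolves would end TTP for good, and could end DOCB, while the same subject stays progression-free for PFS. PFS counts progression or death, so its event should not come after a progression event for the same subject. The report would then hold two progression endpoints that disagree for a reason unrelated to the tumour. TTP would also partly measure the treatment reaction that led the sponsor to replace ORR as the primary endpoint. SAP 4.4 relates TTP and DOCB to IL4R status, prognostic factors, concomitant medication and dosing variables, so the definition carries into those exploratory analyses.

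**Working it through.** The plan gives no figure to reproduce. The check compares definitions, follows one worked subject, and then gives a range under stated assumptions.

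**1. Event rules side by side**

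| Endpoint | SAP | Protocol |
|---|---|---|
| PFS | confirmed (7.7.2) | confirmed (8.1.2); not stated (9.2.5.2) |
| DOR | confirmed (7.7.4) | confirmed (Table 8); not stated (9.2.5.3) |
| DOCB | not stated (7.7.4) | confirmed (Table 8); not stated (synopsis, 9.2.5.3) |
| TTP | first evidence (7.7.4) | no such endpoint |

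The SAP's only PD thresholds are in 7.7.3: an increase of at least 25% in 2D or 40% in 3D. They contain no confirmation step. They appear under the analysis of OS by tumour response, and the TTP paragraph does not cite them.

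**2. Worked subject**

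The PD threshold is met 60 days after catheter placement, and disease control is seen at 90 days. True PD is first seen at 176 days (120 + 56) and confirmed at 204 days (176 + 28). The SAP formulas use event date minus placement date plus 1.

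- TTP, read literally: 60 + 1 = 61 days.
- PFS, dated to the first scan of the confirmed PD: 176 + 1 = 177 days.
- PFS, dated to the confirming scan: 204 + 1 = 205 days.

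TTP is 177 - 61 = 116 days shorter, or 205 - 61 = 144 days shorter. Two PFS values arise because neither document says which scan dates a confirmed progression. If it is the confirming scan, a literal TTP also precedes PFS for PD that is genuinely confirmed.

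**3. Size under assumptions**

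Inputs:
- True progression time is exponential with a median of 4 months (121.75 days), the protocol's null value for PFS, or 6 months (182.625 days), which is assumed.
- A fraction q of 20 to 40% has an early scan recorded as PD and not confirmed. This is also assumed, since the documents say only that some subjects were affected.
- Scans are at Days 30, 60, 90 and 120. The next is at Day 176 (8 weeks later) or Day 180 (the schedule footnote).

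*Six-month progression-free proportion with confirmed PD.* A subject is progression-free at 6 months if true progression comes after the Day 176 or Day 180 scan:
- Median 4 months: 2^(-176/121.75) = 0.367, or 2^(-180/121.75) = 0.359.
- Median 6 months: 2^(-176/182.625) = 0.513, or 2^(-180/182.625) = 0.505.

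*Same proportion with literal TTP.* Every early flare comes before that scan, so the proportion is multiplied by (1 - q):
- Median 4 months: 0.367 x 0.8 = 0.294 and 0.367 x 0.6 = 0.220. The Day 180 grid gives 0.287 and 0.215.
- Median 6 months: 0.513 x 0.8 = 0.410 and 0.513 x 0.6 = 0.308. The Day 180 grid gives 0.404 and 0.303.

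*Share whose TTP event precedes the PFS event.* With the flare equally likely at Day 30, 60 or 90, the share is q times the mean probability that true progression comes after the flare scan:
- Median 4 months: (0.843 + 0.711 + 0.599)/3 = 0.718, so 14% at q = 0.2 and 29% at q = 0.4.
- Median 6 months: (0.892 + 0.796 + 0.711)/3 = 0.800, so 16% and 32%.

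A simulation of 200,000 subjects, with a median of 5 months from progression to death, gave the same figures to within rounding. With q = 0 no TTP event precedes the PFS event.

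**4. Why medians are not quoted**

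With a true median of 4 months, 1 - 2^(-120/121.75) = 49.5% have already progressed by Day 120. A flare rate of 2% adds 0.02 x 50.5% = 1.0%, which takes the total past 50% and moves the observed median back a whole scan, from Day 180 to Day 120. With a 6-month median the same happens at Day 180. Shifts in the median would mostly describe the scan grid.

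**The case against.** The strongest defence is that first evidence is only a dating convention: use the first scan of a PD that is later confirmed, not the confirming scan. The next SAP sentence censors subjects who have not progressed, and protocol 1.4.1 lets an initial PD with no later signs count as non-progression. This reading is possible, and it is what the fix would make explicit. However, the SAP does not state it, SAP 4.3 does not settle it, and the use of *confirmed* for DOR in the same section favours the literal reading.

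Other parts of the defence stand and limit the point:

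- A reader might infer that every pseudo-progression becomes a TTP event. The documents do not support that. Protocol 1.4.1 defines pseudo-progression with no size threshold, so an increase below the PD threshold is not PD. Protocol 8.1.3 uses advanced imaging and/or biopsy to rule pseudo-progression out, so a recognised flare need not be called PD. The SAP makes advanced imaging conditional on available data (stated for ORR), so the safeguard is incomplete.
- A reader might take any TTP shorter than PFS as proof of error. Recorded times can fall in that order under matched definitions: a subject who dies without PD has TTP censored at the last adequate assessment and PFS ending at death. Only the order of event times is anomalous.
- A reader might expect better-covered tumours to flare more, and so expect bias in the TTP relationships with coverage or dose. No passage links flare to coverage.
- TTP is an SAP-only endpoint in the other-efficacy tier, summarised by Kaplan-Meier without a test, and the bias runs against the drug.

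**Conclusion.** The concern holds in a limited form. As literally written, the SAP can count a PD that later imaging cancels as a TTP event, and can end DOCB on it, while PFS does not count it. The mismatch is in the current text and does not depend on any assumption.

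Its size does. If 20 to 40% of subjects have an early unconfirmed PD and the true median is 4 months, the 6-month progression-free proportion by TTP falls from about 36-37% to 29-22%, and the TTP event precedes the PFS event in about 14 to 29% of subjects. With a true median of 6 months the proportion falls from about 51% to between 40-41% and 30-31%. These figures take every assumed flare as recorded PD. They shrink in proportion if fewer subjects flare or if central review recognises flares at the first read.

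The wording should be corrected before the final analysis. It affects lower-tier endpoints and the exploratory analyses built on them. OS, the PFS event definition and the sample size are not affected.

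**What to change.** In SAP 7.7.4:

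1. Define the progression event for TTP and DOCB as PD that is subsequently confirmed under the same m/iRANO rule as PFS. State that a first PD not confirmed on later imaging is not an event.
2. State one dating rule, the first scan of the confirmed PD, and apply it to PFS, DOR, DOCB and TTP. For PFS this settles the date and leaves the event unchanged.
3. If time to first unconfirmed PD is of interest, report it as a supplementary variable under its own name.

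The cost is about one sentence per endpoint, plus the matching programming. No extra scans are needed. The follow-up scans after Days 30, 60 and 90 are already scheduled, and protocol 7.5.3 already calls for repeat assessment after 4 weeks when preliminary progression is seen from Day 120 on.
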